9.5 Planned Interim Analysis, Adaptive Design, and Dose Escalation Committee

Shire's Dose Escalation Committee will be convened consisting of the coordinating principal ophthalmologist and Shire medical monitor. Ad hoc study team members can be included such as biostatistics, pharmacokinetics, drug safety, and clinical operations if needed. The committee will review collective safety data for Cohort A and Cohort B to decide whether Part 2 in the same dose level and Part 1 in the next dose level (concentration) can commence.

An unmasked interim analysis (IA) will be performed after cohorts A1, A2, A3, B1, B2, and B3 have completed through Day 29 of the B3 cohort. Data from sites will be entered into the database, queried, and discrepancies resolved. There is no intention to stop early based on data from the IA. The intent of this IA is to determine if the escalated doses have identified a pharmacodynamically significant safe and tolerable dose(s) for further clinical evaluation.

Team members reviewing the interim analysis will be reviewing unmasked data from cohorts A1, A2, A3, B1, B2, and B3. The SAP will be finalized before data are frozen for this interim analysis.

All cohorts conducted after B3 (ie Part 1 of the study) may be unmasked following completion of Day 29 to permit review of safety, tolerability and the pharmacodynamics effects of each cohort to better inform planning for additional cohorts and further clinical development options for SHP639.

A final unmasked analysis will be conducted when all subjects of the remaining cohorts have completed through Day 29. The Day 88/FU visit is the planned study completion for each subject.

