9.6 Sample Size Calculation and Power Considerations

A sufficient number of subjects will be screened to ensure the enrollment and completion of 84 subjects.

The number of subjects in this study is not based on statistical power considerations because the statistical analyses are primarily descriptive in nature. However, if at least 7 subjects complete each cohort, then there will be at least 65% to 85% probability of observing at least 1 occurrence of any AE with a true incidence rate for a given dose group of at least 15-25%, respectively.

It is estimated that dose escalation will occur for up to 3 dose levels (4 cohorts within each dose level). Each cohort will include 5 subjects randomized to active drug and 2 subjects randomized to placebo for an estimated total of at least 84 subjects.

For each cohort, the number of subjects will be increased as needed based on safety and IOP response. Any cohort can be repeated to confirm findings with regard to safety or IOP response.

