9.8.2.2 Statistical Analysis of Pharmacodynamic Parameters

Descriptive summary statistics for IOP (number of subjects, mean, SD, median, min, and max) will be calculated by dose, cohort, treatment period (single dose or multiple dose; Cohort A only), study day, and time point (for days with multiple assessments per day). Additionally, 95% CIs for each estimate and summary statistics of change from baseline and percentage change from baseline, along with 95% CIs, will be calculated. Pharmacodynamic parameters will be calculated and summarized by dose, cohort, treatment period (single dose or multiple dose; Cohort A only), and study day as applicable.

All IOP data will be listed by dose, cohort, subject, treatment period (single dose or multiple dose; Cohort A only), and study day.

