2. STUDY DESIGN

2.1 General Study Design

This is a multicenter, randomized, double-masked, placebo-controlled, single- and multiple-dose escalation study. Three different SHP639 concentrations will be studied: 0.1%, 0.3%, and 0.6%. There will be up to 12 cohorts in total, 1 cohort for each dose level and different dosing regimen. Each cohort will consist of 7 subjects for a total of 84 subjects in the study. Eligible subjects will be randomized in a 5:2 ratio to receive either SHP639 or placebo, respectively. The anticipated concentrations being studied for each dosing regimen are presented in the study schema in Figure 1.

A sufficient number of subjects will be screened and enrolled to ensure that at least 6 of 7 subjects complete each treatment in their assigned cohort. In the event that a sufficient number of subjects do not complete a cohort, replacement subjects may be enrolled. Each replacement subject will follow the same screening procedures and randomization sequence as the subject who is discontinued, regardless of when the subject discontinued.

Figure 1 Study Schema

Solid arrows are not drawn to scale and indicate both the flow of dosing regimens and the occurrence of a dose escalation meeting.

BID=twice daily; MDTP=multiple-dose treatment period; QD=once daily; QID=4 times daily; SD=single dose; SDTP=single-dose treatment period; TID=3 times daily

^a Dose escalation meetings will convene when 6 out of 7 subjects have completed Day 14 in the previous cohort's multiple-dose administration. This does not include the decision to move from Cohort B to C. Decisions will include safety, tolerability, and intraocular pressure data.

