2.3 Determination of Sample Size

A sufficient number of subjects will be screened to ensure the enrollment and completion of 84 subjects.

The number of subjects in this study is not based on statistical power considerations because the statistical analyses are primarily descriptive in nature. However, if at least 7 subjects complete each cohort, then there will be at least 65% to 85% probability of observing at least 1 occurrence of any AE with a true incidence rate for a given dose group of at least 15% to 25%, respectively.

It is estimated that dose escalation will occur for up to 3 dose levels (4 cohorts within each dose level). Each cohort will include 5 subjects randomized to active drug (SHP639) and 2 subjects randomized to placebo for an estimated total of at least 84 subjects.

For each cohort, the number of subjects will be increased as needed based on safety and IOP response to investigational product. Any cohort can be repeated to confirm findings with regard to safety or IOP response to investigational product.

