3.1.2 Secondary Objectives

The secondary objective of this study is to evaluate reduction of IOP, as a PD biomarker, following different SHP639 dosing regimens.

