12.5 Statistical Analysis of Pharmacodynamic Data

Absolute IOP, IOP reduction from baseline, and percentage of IOP reduction from baseline will be listed by dose, cohort, subject, treatment period (single dose or multiple dose; Cohort A only), eye (study eye and non-study eye), study day and sample nominal time point. Descriptive summary statistics for absolute IOP, IOP reduction from baseline, percentage of IOP reduction from baseline, E_{max}, TE_{max}, AUEC_{0-t}, AUEC_{0-τ}, and AUEC_{0-∞} (n, arithmetic mean, SD, 95% CI, median, maximum, minimum, geometric mean and geometric CV%) will be calculated by dose, cohort, treatment period, eye (study eye and non-study eye), study day, and sample nominal time point (for days with multiple assessments per day).

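### Neither document estimates a SHP639-minus-placebo difference in IOP; the plan reports only within-group change from a baseline that subjects were partly selected on

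*SAP*

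**What the plan says.** SAP 3.1.2: "The secondary objective of this study is to evaluate reduction of IOP, as a PD biomarker, following different SHP639 dosing regimens". No comparator is named.

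SAP 2.1: "Eligible subjects will be randomized in a 5:2 ratio to receive either SHP639 or placebo, respectively". SAP 2.3 gives the numbers: "Each cohort will include 5 subjects randomized to active drug (SHP639) and 2 subjects randomized to placebo".

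SAP 12.5 lists the PD statistics as "n, arithmetic mean, SD, 95% CI, median, maximum, minimum, geometric mean and geometric CV"%, and these "will be calculated by dose, cohort, treatment period, eye (study eye and non-study eye), study day, and sample nominal time point". Protocol 9.8.2.2 is of the same kind: "summary statistics of change from baseline and percentage change from baseline, along with 95% CIs, will be calculated". SAP 12.4 and 12.6 add profile plots, a box plot by dose, and PK-PD scatter plots.

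IOP is also tabulated as a safety variable on the Safety set (SAP 11.6.2.9), by eye and treatment, as value, change and percentage change. SAP 11 pools placebo by dosing regimen for MDTP ocular summaries. SAP 12.5 has no pooling rule.

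In the SAP 16 output list, the PD-set IOP tables (14.2.3.2.1 and 14.2.3.2.2) are marked N for the interim. The Safety-set MDTP IOP tables (14.3.7.9.7 to 14.3.7.9.12) are marked Y. No listed output is a difference from placebo, and Protocol 9.10 plans no other analyses.

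**The concern.** A mean change from baseline within an active group mixes the drug effect with everything else that moves IOP over four weeks. One such component is built into this design. Protocol 4.1, criterion 4, admits subjects on Day -1 IOP of at least 24 mmHg at 8:00 AM and at least 22 mmHg at 10:00 AM in at least one eye. SAP 11.6.2.9 and 12.4 define baseline at each time point as the mean of Days -2 and -1, so the qualifying reading is half of the baseline. SAP 2.4 then normally takes as study eye the one with the higher baseline. Selecting on a high reading and measuring change from it produces some fall without treatment. Time-matching the baseline handles the diurnal pattern but not this.

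The randomized placebo group carries the same selection, so a difference from placebo removes the artefact in expectation. The plan leaves that subtraction to the reader's eye and gives it no interval. Yet IOP matters to decisions: Protocol 9.5 says the interim asks whether escalation has found a pharmacodynamically active dose that is also safe and tolerable, and Protocol 9.6 lets cohorts be enlarged or repeated on IOP response.

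**Working it through.** **The plan's own figures.** The documents give no IOP SD, precision or power. Their one probability statement concerns adverse events in 7 subjects: 1 - 0.85^7 = 67.9% and 1 - 0.75^7 = 86.6%, consistent with the stated lower bounds of 65% and 85%. It has no bearing on IOP.

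**Inputs.** 5 active and 2 placebo per cohort (SAP 2.3). Three cohorts per regimen give 3 × 2 = 6 placebo. QID without Cohort D1, which is not enrolled (Protocol Table 10), gives 4. Eleven cohorts give 22, or 24 if the repeat of B3 also had 2. The SD of IOP change is assumed to be 3 mmHg, range 2-4.

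**Within-group 95% half-width**, t(0.975, n-1)/√n, in sample SDs:

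- Placebo n = 2: 12.706/√2 = 8.98
- Active n = 5: 2.776/√5 = 1.24
- Placebo n = 6, pooled by regimen: 2.571/√6 = 1.05

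**SHP639-minus-placebo 95% half-width**, t(0.975, df) × √(1/n1 + 1/n2) × SD, before any baseline adjustment:

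| Comparison | df | SD units | mmHg at SD 3 (SD 2 to 4) |
|---|---|---|---|
| 5 v 2, one cohort | 5 | 2.571 × √0.700 = 2.15 | 6.5 (4.3-8.6) |
| 5 v 4, QID without D1 | 7 | 1.59 | 4.8 (3.2-6.3) |
| 5 v 6, pooled by regimen | 9 | 1.37 | 4.1 (2.7-5.5) |
| 5 v 6, variance pooled within regimen | 17 | 1.28 | 3.8 (2.6-5.1) |
| 5 v 22, pooled over cohorts | 65 | 1.997 × √0.2455 = 0.99 | 3.0 (2.0-4.0) |

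The 17 df are 21 subjects less 4 groups. The 65 df are 77 subjects less 12 groups.

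**Gain.** Pooling over all cohorts instead of by regimen narrows the interval by 4.1/3.0 = 1.4, or by 3.8/3.0 = 1.3 once variance is pooled within regimen.

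**Regression to the mean.** Its size cannot be computed, because the documents give no between-day correlation of IOP. The direction follows from the entry threshold. The exclusion of IOP above 32 mmHg trims the other tail and offsets some of it. No figure is claimed.

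**The case against.** The strongest reply is that this is a small Phase 1 study, declared primarily descriptive, with a secondary objective that names no comparator and no intention to stop early at the interim. On that view nothing is inconsistent. That stands as far as it goes: this is a gap in estimation, not a broken power claim. But a difference with a confidence interval is itself descriptive, and SAP 12.3 already fits models with confidence intervals for the PK data.

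Three stronger readings are tempting, and the documents do not support them.

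- A reader might infer that the interim rested on placebo rows of 2 subjects. The tables with those rows are marked N for the interim. The interim IOP tables fall under pooling by regimen, with about 6 placebo subjects.
- A reader might infer that the placebo group goes unused for IOP. It is tabulated and plotted by treatment; what is missing is the contrast.
- A reader might take 6.5/3.0, about 2.2-fold, as the benefit of pooling placebo. That ratio also includes the move from 5 to 65 df. At 65 df throughout, 5 v 2 gives 1.997 × 3 × √0.700 = 5.0, so placebo pooling alone gives 5.0/3.0 = 1.7. Against the SAP's own regimen pooling the gain is only 1.3 to 1.4.

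Timing also counts. The SAP carries the date 30 August 2018. SAP 13 places the Part 1 interim in November 2017 and reports the B3-repeat interim as done in June 2018. A model added now cannot inform those reviews and is post hoc for those cohorts.

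Finally, the title of Table 14.2.3.2.1 says by treatment, so it might be programmed with pooled placebo. The text of SAP 12.5 says dose and cohort.

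**Conclusion.** The point holds as a gap in estimation. No section, model or listed output in either document gives a SHP639-minus-placebo difference in IOP, and the within-group change reported instead is open to regression to the mean. The ±8.98 SD interval describes only the PD-set summaries at the planned 2 placebo subjects. An SD from two values is itself very unstable, and replacements or a repeated cohort could raise n (n = 4 gives ±1.59 SD). With the SAP's existing pooling by regimen, a placebo difference would carry a half-width of about 4 mmHg at the assumed SD of 3. That is wide, but it answers the secondary objective where the present summaries do not. The mmHg figures scale directly with the assumed SD. Pooling assumes a similar placebo response across the pooled cohorts, since randomization protects the comparison only within a cohort.

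**What to change.** Add to SAP 12.5, for the study eye in the MDTP:

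- An analysis of covariance of IOP change at each time point, and of the diurnal mean already defined in SAP 11.6.2.9, with treatment group as factor and the matching baseline IOP as covariate. Report SHP639 minus placebo with 95% CI for each dose and regimen.
- Main analysis: placebo pooled by regimen, as in SAP 11. Supportive analysis: placebo pooled over all cohorts. Show placebo means by regimen beside it, noting that 4 to 6 subjects per regimen are a weak check on the pooling assumption.
- A statement that these are estimates, not powered tests, and that they are post hoc for every cohort unmasked before the amended SAP is signed.

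Keep the by-cohort descriptive tables. The cost is SAP wording and one model-based table; no new data or subjects are needed. The downside is the assumption of similar placebo response across the pooled cohorts.

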12.6 Analyses of Pharmacokinetic/Pharmacodynamic Relationships

If data permit, a potential relationship between concentrations of SHP639 ophthalmic solution and percentage of IOP reduction from baseline will be explored graphically using box plots; the

relationship between the PK and PD parameters for percentage of IOP reduction from baseline measurement will be presented graphically using scatter plots with regression line and the corresponding R^2 values.

13. INTERIM ANALYSIS

Shire's Dose Escalation Committee will be convened consisting of the coordinating principal investigator and Shire medical monitor. Ad hoc study team members can be included such as biostatistics, pharmacokinetics, drug safety, and clinical operations if needed. The committee will review collective safety data for Cohort A and Cohort B to decide whether Part 2 in the same dose level and Part 1 in the next dose level (concentration) can commence. An interim analysis is planned for November, 2017. The safety and efficacy summaries for Part 1 of the study will be created using clean data, for the purpose of regulatory filing in January 2018. Shire and PPD teams will be unmasked to treatments for subjects in Cohorts A and B as of the interim analysis, but will remain masked to treatments for subjects in Cohorts C and D until study completion.

The interim analysis will consist of non period specific outputs (including but not limited to disposition, demographics, protocol violations, concomitant medications) and all MDTP outputs. Outputs to be generated for the interim analysis are denoted in the list of outputs in Section 16.

Following changes introduced in protocol amendment 3, all cohorts conducted after B3 (eg Part 1 of the study) may be unmasked following completion of Day 29 to permit review of safety, tolerability and the pharmacodynamics effects of each cohort to better inform planning for additional cohorts and further clinical development options for SHP639. Interim analysis of data from the repeat of Cohort B3 was conducted in June, 2018. Outputs for this interim analysis are denoted in the list of outputs in Section 16.

A final unmasked analysis will be conducted when all patients of the remaining cohorts have completed through Day 29. The Day 88/FU visit is the planned study completion for each subject.

14. COMPUTER METHODS

All statistical analyses will be performed using SAS[®] Version 9.3 or higher (SAS Institute, Cary, NC 27513) on a suitably qualified environment.

15. DATA HANDLING CONVENTIONS

15.1 General Data Reporting Conventions

Continuous variables will be summarized using the following descriptive statistics: n, mean, median, standard deviation, minimum, maximum. Categorical and count variables will be summarized by the number of subjects (n) and the percent of subjects in each category. Percentages will be presented as whole numbers.

15.2 Missing Date of Investigational Product

When the date of the last dose of investigational product is missing for a subject in the Safety set, all efforts should be made to obtain the date from the investigator. If it is still missing after all efforts, then the last visit date when investigational product was returned will be used in the calculation of treatment duration.

15.3 Missing Date Information for Prior or Concomitant Medications

For prior or concomitant medications, including rescue medications, incomplete (ie, partially missing) start date and/or stop date will be imputed. When the start date and the stop date are both incomplete for a subject, impute the start date first.

15.3.1 Incomplete Start Date

The following rules will be applied to impute the missing numerical fields. If the stop date is complete and the imputed start date is after the stop date, then the start date will be imputed using the stop date.

Missing day and month

- If the year of the incomplete start date is the same as the year of the date of the first dose of investigational product, then the day and month of the date of the first dose of investigational product will be assigned to the missing fields
- If the year of the incomplete start date is before the year of the date of the first dose of investigational product, then December 31 will be assigned to the missing fields
- If the year of the incomplete start date is after the year of the date of the first dose of investigational product, then 01 January will be assigned to the missing fields.

Missing month only

- The day will be treated as missing and both month and day will be replaced according to the above procedure.

Missing day only

- If the month and year of the incomplete start date are the same as the month and year of the date of the first dose of investigational product, then the day of the date of the first dose of investigational product will be assigned to the missing day

- If either the year is before the year of the date of the first dose of investigational product or if both years are the same but the month is before the month of the date of the first dose of investigational product, then the last day of the month will be assigned to the missing day
- If either the year is after the year of the date of the first dose of investigational product or if both years are the same but the month is after the month of the date of the first dose of investigational product, then the first day of the month will be assigned to the missing day.

15.3.2 Incomplete Stop Date

The following rules will be applied to impute the missing numerical fields. If the date of the last dose of investigational product is missing, then replace it with the last visit date. If the imputed stop date is before the start date (imputed or non-imputed start date), then the imputed stop date will be equal to the start date.

Missing day and month

- If the year of the incomplete stop date is the same as the year as of the date of the last dose of investigational product, then the day and month of the date of the last dose of investigational product will be assigned to the missing fields
- If the year of the incomplete stop date is before the year of the date of the last dose of investigational product, then 31 December will be assigned to the missing fields
- If the year of the incomplete stop date is after the year of the date of the last dose of investigational product, then 01 January will be assigned to the missing fields.

Missing month only

- The day will be treated as missing and both month and day will be replaced according to the above procedure.

Missing day only

- If the month and year of the incomplete stop date are the same as the month and year of the date of the last dose of investigational product, then the day of the date of the last dose of investigational product will be assigned to the missing day
- If either the year is before the year of the date of the last dose of investigational product or if both years are the same but the month is before the month of the date of the last dose of investigational product, then the last day of the month will be assigned to the missing day
- If either the year is after the year of the last dose of investigational product or if both years are the same but the month is after the month of the date of the last dose of investigational product, then the first day of the month will be assigned to the missing day.

15.4 Missing Date Information for Adverse Events

For AEs, the default is to only impute incomplete (eg, partially missing) start dates. Incomplete stop dates may also be imputed when calculation of the duration of an AE is required per the protocol. If imputation of an incomplete stop date is required, and both the start date and the stop date are incomplete for a subject, impute the start date first.

15.4.1 Incomplete Start Date

Follow same rules as in Section 15.3.1.

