3.1.4.2 Cohorts A1-A3: Multiple-dose Treatment Period

After completion of the assessments scheduled for Day 2 of the SDTP, subjects will enter a washout period. The duration of the washout period will last between 3 and 14 days. A dose escalation meeting will occur prior to the advancement to each cohort (refer to Section 6.2.3.2 for additional details). For each cohort, following a decision to commence the MDTP, subjects will attend the site on Days -2 and -1 to undergo the scheduled safety and ophthalmic assessments. In Cohorts A1, A2, and A3 MDTP, all subjects will be administered investigational product in both eyes. The same dose concentration that was administered during the SDTP of the relevant cohort (A1, A2, or A3) will be administered during the MDTP QD for the next 28 days. Subjects are to place 1 drop in each eye at approximately the same time each day. Refer to Table 1 and Section 6.2.3 for additional details.

Subjects will be admitted to the site on Day 1 and will be discharged after completion of all Day 2 assessments. On Days 7, 14, and 21, subjects will return to the site as described in Table 1. On Day 26, subjects will be readmitted to the site. On Day 27, subjects will continue to self-administer investigational product while undergoing the scheduled assessments. The last dose will be administered on the morning of Day 28. After completion of the assessments scheduled for Day 29, subjects will then be discharged from the site.

Subjects will receive a follow-up telephone call approximately 7 days after being discharged from the site. They will return to the site to undergo antidrug antibody (ADA) sampling approximately 60 days after the last dose of investigational product (Day 88).

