^m Drop comfort assessments will be performed immediately and 1, 2, and 3 minutes after instillation of the investigational product; to be assessed at morning doses only. If the score is not ≤ 3 at minute 3, the drop comfort assessment should be repeated at minutes 5, 10, and 15 until the score is ≤ 3 . If the score is >3 at minute 15, it should be recorded as an adverse event.

ⁿ If BCVA decreases by 6 or more letters, then a dilated posterior segment examination should be performed.

^o Manifest refraction should be repeated if the BCVA in either eye decreases by 10 or more letters.

^p Conjunctival redness will be evaluated using the Efron scale.

^q SDTP dosing (Cohort A only): investigational product (SHP639 ophthalmic solution or placebo) will be administered once on the morning of Day 1. MDTP dosing: Cohort A=once daily, Cohort B=twice daily, Cohort C=3 times daily, Cohort D=4 times daily; the final dose will be administered on the morning of Day 28. Dose administration will occur during waking hours.

^r The Day 88 visit is 60 days post last dose (Day 28 of MDTP).

^s For Screening, MWOA, and Day 29 visits only one round of ophthalmic assessments needs to be done in the morning.

^t At check-in for overnight stays the following assessments will be performed: physical exam, drugs of abuse screening, alcohol breathalyzer, vital signs, hematology, chemistry, urinalysis, and a single ECG.

^u The Day 88/FU visit is labeled "Day 88" based on a subject's duration of participation from Day 1 (1st dose) of the MDTP. Subjects in cohort A1, A2, and A3 will have been in the study for a longer duration due to the SDTP.

^v At screening IOP may be done at any time during the day. At MWOA (D-14), IOP should be done at 10:00am +3 hours. IOP only needs to be done at one time during screening, MWOA, and Day 29.

Table 2 Detailed Schedule of Events – Cohort A

Assessment	Days Performed (Screening-D29) ^f	Predose/ Morning ^a	0 m	30 m	1 h	2 h	3 h	4 h	6 h	8 h	12 h
		Gonioscopy ^c	SCR, D29.	X							
Specular microscopy, noncontact	SCR. SDTP: D-1, D2. MDTP: D-1, D14, D29.	X									
Corneal pachymetry	SCR. SDTP: D-1, D1, D2. MDTP: D-1, D1, D2, D7, D14, D29.	X			X	X		X			X
Antidrug Ab blood sampling	D-2, D14, D29, D88/FU	X									
Drugs of abuse	SCR, D-14, SDTP: D-2, MDTP: D-2 and D-1, D1, D14, D21, D26.	X									
Alcohol breath test	SCR (D-42), SCR (D-14). SDTP: BL (D-2), MDTP: BL (D-2 and D-1), D1, D14, D21, D26.	X									

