11. SAFETY ANALYSES

The safety analysis will be performed using the Safety set. Safety and tolerability will be assessed by monitoring AEs, vital sign measurements, clinical laboratory test values, ECG readings, antidrug antibodies, drop comfort assessment, and ophthalmologic examinations. SDTP and MDTP outputs will be summarized separately. For SDTP, data will be summarized for two periods:

- a. Dosing period only: Day 1 SDTP – Day 2 SDTP
- b. Dosing period and washout period: Day 1 SDTP up to First Dose MDTP

For SDTP, ocular summaries will be presented for the study eye and the non-study eye. For MDTP, all ocular summaries will be presented for the study eye, the non-study eye, and for either eye. For summarization by either eye, the eye with the less favorable response at the given timepoint will be summarized which may result in different eyes being summarized at different visits. Adverse events and selected ocular assessments summaries will also be presented for both eyes. For summarization by both eyes, subjects with events or assessments occurring in both eyes will be included. In the MDTP, ocular summaries will be presented first by dose regimen then by dose level and placebo subjects will be pooled by dosing regimen. (eg, QD placebo subjects will be pooled together, BID placebo subjects will be pooled together, TID placebo subjects will be pooled together, and QID placebo subjects will be pooled together.) All subjects in the Safety set (including placebo-treated subjects) within a regimen will also be presented. (For example, all active QD doses and QD placebo patients will be combined for the QD dosing regimen summaries.)

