15.4.3 Incomplete Start/Stop Time

There is no imputation for missing start/stop time for AEs. In such cases, only the date part will be used to compare with the dosing date. If an AE start date is before the first dose of MDTP, it will be summarized in the SDTP outputs; if an AE start date is on or after the first dose of MDTP, it will be summarized in the MDTP outputs.

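### Partial AE start dates in Cohort A are anchored to the single dose, so some multiple-dose AEs fall into the single-dose tables

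*SAP*

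**What the plan says.** SAP 15.4.1 has a single line for incomplete AE start dates: "Follow same rules as in Section 15.3.1". Section 15.3.1 was written for prior and concomitant medications. Its branches that matter here are:

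- Day missing, onset in the same month and year as the first dose: "then the day of the date of the first dose of investigational product will be assigned to the missing day".
- Day missing, onset in a later month: "then the first day of the month will be assigned to the missing day".
- Day and month missing, onset in the same year as the first dose: "then the day and month of the date of the first dose of investigational product will be assigned to the missing fields".

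None of these says which treatment period's first dose is meant. The one override in 15.3.1 acts when the imputed start falls after a complete stop date.

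Cohort A has two treatment periods. The first begins with one drop in one eye; SAP 2.2 states "SDTP dosing (Cohort A only): investigational product (SHP639 ophthalmic solution or placebo) will be administered once on the morning of Day 1". A washout follows before the MDTP; Protocol 3.1.4.2 states "The duration of the washout period will last between 3 and 14 days".

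The period is then assigned from the (imputed) date. SAP 15.4.3: "If an AE start date is before the first dose of MDTP, it will be summarized in the SDTP outputs". SAP 11 sets the same boundary for the longer of its two single-dose summaries: "Dosing period and washout period: Day 1 SDTP up to First Dose MDTP".

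**The concern.** Placing an uncertain onset on the first-dose date is normally the cautious choice, because it makes the event treatment-emergent. That works in Cohorts B, C and D, which have one treatment period. In Cohort A the anchor lies in the earlier period, so the rule can take an event from 28 days of once-daily dosing in both eyes and show it as a reaction to one drop in one eye, or to its washout.

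Safety and tolerability are the primary objective, and SAP 11 summarises the two periods separately, so period attribution matters. The effect also runs against the SAP's other rules for incomplete AE data: 15.5 and 15.6 set missing on-treatment severity to severe and missing relationship to related. In addition, SAP 16 marks the MDTP overall, system-organ-class and severity AE tables for the interim analysis but none of the SDTP AE tables. A moved event would therefore be absent from the interim AE summaries and appear only in the AE listing.

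**Working it through.** The documents give no figure on this point, so there is nothing to reproduce. The check follows the rules as written.

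**1. Mechanism.** Take a true MDTP event with only the day missing.

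- Onset month = month of MDTP Day 1, SDTP dose in that same month: imputed to SDTP Day 1, which is before MDTP Day 1. Moved.
- Onset month = month of MDTP Day 1, SDTP dose in the previous month: imputed to the 1st, which is before MDTP Day 1 unless MDTP Day 1 is itself the 1st. Moved.
- Onset in a later month: imputed to the 1st of that month, which is after MDTP Day 1. Not moved.

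The stop-date override does not help. A true MDTP event stops on or after MDTP Day 1, so its stop date is never before the imputed start. If day and month are both missing and the year is the first-dose year, the event always goes to SDTP Day 1.

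**2. Example (dates assumed).** SDTP Day 1 on 5 June, MDTP Day 1 on 15 June, dosing to 12 July. Onsets on 15-30 June (16 days) are imputed to 5 June and move; onsets on 1-12 July (12 days) stay. Share moved: 16/28 = 57%. In a 30-day month the share is 0% if MDTP Day 1 is the 1st, 28/28 = 100% if the 2nd, and 1/28 = 4% if the 30th.

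**3. Average share.** Assumptions, not in the documents: start dates even over the calendar, and partial dates equally likely at every onset. With mean month length M = 365/12 = 30.4, an onset on MDTP day d moves when MDTP Day 1 falls on day c of its month with c ≥ 2 and c + d − 1 ≤ M. That is M − d of the M possible start days, so the share is 1 − d/M for d < M. The washout length does not enter.

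- Even onset over Days 1-28 (mean d = 14.5): 1 − 14.5/30.4 = 0.523.
- Enumerating 365 start dates, SDTP-to-MDTP gaps of 5-16 days (and 7-18, if Days -2 and -1 lie outside the washout) and every onset day under the exact rule also gives 0.523.

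| Onset days | Share moved |
|---|---|
| 1-7 | 87% |
| 8-14 | 64% |
| 15-21 | 41% |
| 22-28 | 18% |
| 29-35 | 1% |

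- Treatment-emergent window (SAP 11.1: last dose on Day 28, plus 7 days = Day 35), even onset: (28 × 0.523 + 7 × 0.010)/35 = 0.42.
- Front-loaded onset over Days 1-35 with an assumed 7-day half-life: 0.69.

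**4. Where moved events land.** For even onset over Days 1-28 and gaps of 5-16 days, about 28% of all missing-day MDTP events land in the SDTP Day 1-2 tables (43% at a 5-day gap, 15% at a 16-day gap). The rest of the 52% appear only in the dosing-plus-washout tables.

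**5. Reverse direction.** Under the current rule 0% of true SDTP or washout events move into the MDTP. If every Cohort A event were re-anchored to the first MDTP dose, about 79% of true SDTP or washout events with a missing day would move the other way.

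**6. Weight of one event.** An active group has 5 planned subjects, so one subject is 1/5 = 20 percentage points. Once-daily placebo is pooled over A1-A3 (3 × 2 = 6 planned), so one subject is 1/6, about 17 points.

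**The case against.** The best reply is that first dose may have been meant per period. SAP 9.1 and 9.2 use a similar phrase for MDTP exposure and compliance. But both name the MDTP in setting out the calculation, and 15.4.3 names the MDTP first dose when it means it; 15.3.1 does neither. The literal reading is the stronger one, and if the other was intended the SAP should say so.

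A second reply is that partial dates will be scarce where the rule does most harm. Subjects are in the unit on Days 1-2 and from the evening of Day 26 to Day 29, attend on Days 7, 14 and 21, and are asked about AEs at each visit (Protocol 7.2.2.4). Recall gaps are longest after Day 29, where almost nothing moves. Spread evenly over Days 1-88, the share is only 17%, though onsets after Day 35 are not treatment-emergent. This stands: no single percentage can be fixed from the documents, and the absolute number is probably small.

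A reader might infer that half of all Cohort A multiple-dose AEs are misplaced, or that each one shifts its cohort by 20 points. Neither is supported. Only events with partial dates are affected, at a rate the documents do not give. The 20 points need an active subject with no other event counted in that row, since SAP 11.1 counts a subject once. Nor is any event lost, and because the rule applies equally to SHP639 and placebo it has no built-in bias between arms.

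**Conclusion.** The point holds as a small defect in a stated rule. Followed literally, SAP 15.4.1, 15.3.1 and 15.4.3 assign some Cohort A multiple-dose AEs to the wrong period, and no other section corrects this. The shift is one-directional: it understates once-daily multiple-dose incidence and overstates single-dose incidence. Its relative size is 42% to 69% of missing-day events in the treatment-emergent window under the two timing assumptions tried, and 52% for even onset over the dosing days. It reaches 100% when day and month are both missing in the first-dose year. The scope is 21 planned subjects and partial-date events only, and the effect on the final tables could be nil.

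**What to change.** Add to SAP 15.4.1: for Cohort A, if an AE with a partial start date was first reported after the first MDTP dose (taken from the recorded AE visit or treatment period), and the partial date and any stop date are compatible with onset on or after that dose, apply the 15.3.1 rules with the first MDTP dose date as the anchor. All other Cohort A AEs keep the SDTP anchor. Both conditions are needed, because re-anchoring every Cohort A event would create the larger reverse error shown above.

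The cost is one sentence and a small programming change. SAP 11.1 already lists AEs by treatment period, visit and day, so the information should be available, but the sponsor should confirm that the recorded visit shows when the event was first reported. A few washout events reported late may be counted in the MDTP. The SAP is dated 30 August 2018, and SAP 13 planned unmasking of Cohorts A and B at an interim in November 2017. The change should therefore be recorded as made after that point, and any difference from interim tables footnoted.
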